## 1 PROTOCOL SUMMARY

### 1.1 SYNOPSIS

Title:	Postpartum progestin-only pill use and breastfeeding study
Study Description:	This study will assess the impact of early initiation (less than one week postpartum) and delayed initiation (4 weeks postpartum) of two types of progestin-only contraceptive pills on maternal, breastmilk, and infant outcomes. This is a placebo-controlled randomized controlled trial enrolling dyads of mothers and their newborn babies. We will explore if the type and timing of initiation of pills is acceptable to the user with minimal side effects, impacts the supply or composition of breastmilk, and/or affects infant growth.
Aims:	Specific Aim: To determine whether the type of progestin used (drospirenone in drospirenone-containing progestin-only pills (d-POPs) vs. norethindrone in norethindrone-containing progestin-only pills (n-POPs)) or the timing of progestin initiation (early vs. delayed) affects: Aim 1a Maternal: the duration of exclusive breastfeeding continuation or the rates and types of breastfeeding supplementation over 8 weeks postpartum. Aim 1b Maternal: the proportion of mothers using progestin-only pills at 8 weeks postpartum. Aim 2 Milk: the composition of breastmilk (fat, protein, carbohydrates) at 4 weeks postpartum. Aim 3 Infant: infant growth (weight, length, and head circumference) from birth to 4 weeks.
Study Population:	Postpartum women who delivered an infant within the previous 7 days
Description of Sites	University of California, San Diego (UCSD)
Enrolling Participants:	
Study Duration:	1 year
Participant Duration:	8 weeks

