## 2 INTRODUCTION

### 2.1 STUDY RATIONALE

Drospirenone-containing progestin-only pills (d-POPs) may be an acceptable alternative to Norethindrone-containing progestin-only pills (n-POPs) in the postpartum period when initiated either a week or month after delivery with fewer side effects and no impact on breastfeeding, breastmilk, and infant outcomes. Providing women with more options of safe, effective postpartum (PP) contraception has the potential to reduce unintended pregnancy and short inter-pregnancy intervals, thereby decreasing maternal and infant morbidity and mortality.

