Until recently, POPs containing 0.35 mg daily of the oral progestin Norethindrone (n-POPs) have been the only available POP (Table 1). Norethindrone is a variant of progestin derived from testosterone. N-POPs do not consistently inhibit ovulation; the contraceptive mechanism of action is primarily through progestin effects on the cervical mucous and endometrium. They require daily use with a narrow window of time for intake to maintain efficacy and are associated with unpredictable vaginal bleeding patterns and acne. Fewer than half of women who intend to use n-POPs PP use the method at 3 months. Women who choose n-POPs for PP contraception are significantly more likely to have a short IPI compared to women choosing all other reversible methods.

Drospirenone is a novel progestin derived from spironolactone (Table 1). POPs containing 4 mg of oral drospirenone (d-POPs) became available for use in the U.S. in 2019. D-POPs consistently suppress ovulation and allow for a wider missed-pill window and cyclic use with hormone-free days which offer the potential to improve ease of use and to decrease irregular bleeding. Unlike norethindrone, drospirenone has anti-androgenic properties and should not exacerbate acne and may improve it. The efficacy of d-POPs among non-breastfeeding women is similar to combined estrogen-progestin pills. However, little is known about the effect of d-POPs on breastfeeding performance or PP contraceptive use, efficacy, or side effects among PP women.

Table 1: Progestin types available as progestin-only pills for contraception in the United States

Progestin	Progestin Classification	Available in U.S.	Hormone-free days, 28-day cycle	Androgen effect	Metabolized into Ethinyl Estradiol
Norethindrone	19-nor testosterone, Estrane	1970	None	Medium-high	Small amount
Drospirenone	Spironolactone	2019	4	Antiandrogenic	None

D-POPs are promoted for use while breastfeeding despite a lack of data on the effect of d-POPs on breastfeeding or infant outcomes. The package insert states, “no effects on breastfed infants are

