## 6 STUDY INTERVENTION

### 6.1 STUDY INTERVENTION

Group 1: Initiation of d-POPs 120-160 hours after delivery (N=10)

Group 2: Initiation of n-POPs 120-160 hours after delivery (N=10)

Group 3: Initiation of d-POPs 4 weeks after delivery (N=10) [placebo starting 120-160 hours, continuing for 28 days]

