#### 8.3.4 TIME PERIOD AND FREQUENCY FOR EVENT ASSESSMENT AND FOLLOW-UP

The occurrence of an adverse event (AE) or serious adverse event (SAE) may come to the attention of study personnel during study visits and interviews of a study participant presenting for medical care, by communication from the participant to the study team, or upon review by a study monitor.

All AEs including local and systemic reactions not meeting the criteria for SAEs will be captured. Information to be collected includes event description, time of onset, clinician's assessment of severity, relationship to study product (assessed only by those with the training and authority to make a diagnosis), and time of resolution/stabilization of the event. All AEs occurring while on study must be documented appropriately regardless of relationship. All AEs will be followed to adequate resolution.

Any medical condition that is present at the time that the participant is screened will be considered as baseline and not reported as an AE. However, if the study participant's condition deteriorates at any time during the study, it will be recorded as an AE. Changes in the severity of an AE will be documented to allow an assessment of the duration of the event at each level of severity to be performed. AEs characterized as intermittent require documentation of onset and duration of each episode.

At each study visit, the investigator will inquire about the occurrence of AE/SAEs since the last visit. Events will be followed for outcome information until resolution or stabilization.

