### 9.4.4 SAFETY ANALYSES

AEs and SAEs will be recorded by the study team when they become aware. Adverse events leading to premature discontinuation from the study intervention and serious treatment-emergent AEs will be presented in a table.

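### The safety table in section 9.4.4 omits non-serious adverse events in women who keep taking the pill, so side effects other than vaginal bleeding have no planned summary

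*Combined protocol and SAP*

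**What the plan says.** Section 9.4.4 is the whole of the planned safety analysis and has two sentences. On recording: "AEs and SAEs will be recorded by the study team when they become aware". On output: "Adverse events leading to premature discontinuation from the study intervention and serious treatment-emergent AEs will be presented in a table". It mentions no split by arm, and the documents do not define treatment-emergent for an arm that begins on placebo.

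Section 8.3.4 collects much more than this table shows: "All AEs including local and systemic reactions not meeting the criteria for SAEs will be captured". For each event it asks for a description, onset, severity, relationship and resolution. It also provides for active enquiry: "At each study visit, the investigator will inquire about the occurrence of AE/SAEs since the last visit".

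Side effects are part of the stated interest. The synopsis says "We will explore if the type and timing of initiation of pills is acceptable to the user with minimal side effects". Section 2.1 suggests that drospirenone pills may be an acceptable alternative "with fewer side effects and no impact on breastfeeding, breastmilk, and infant outcomes". Section 2.2 says that norethindrone pills "are associated with unpredictable vaginal bleeding patterns and acne", and that drospirenone should not worsen acne and may improve it.

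For Group 3, section 6.1 specifies "placebo starting 120-160 hours, continuing for 28 days", followed by drospirenone pills.

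**The concern.** The plan collects all adverse events and then reports two subsets: the serious ones and those that made a woman stop. A mother who develops acne, headache or low mood and carries on with her capsules is recorded under 8.3.4 but appears in no planned safety output. These are the events from which a tolerability difference between two contraceptive pills could be described.

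The synopsis question about side effects by pill type and timing would therefore be answered only in part: by bleeding days, by serious events and by events that led to stopping. Section 2.2 makes acne a point of difference between the two progestins, yet acne has no planned summary.

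The table is also the only planned safety summary. Section 8.2 plans no DSMB, and section 10.1.3 leaves oversight with the principal investigator. Section 2.2 says that the pilot is meant to inform a larger trial, for which event frequencies by arm would be useful.

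**Working it through.** The plan states no figure on this point, so the main check sets the sections side by side. The arithmetic afterwards is for scale.

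**1. What is collected against what is reported**

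| Event | Where collected | Planned output |
|---|---|---|
| Serious, treatment-emergent | 8.3.4 | 9.4.4 table; split by arm not stated |
| Non-serious, led to stopping the pill | 8.3.4 | 9.4.4 table; split by arm not stated |
| Vaginal bleeding days | Section 3, at 4 and 8 weeks; 8-week survey in 8.1 | Covered by the Group 1 v 2 and 1 v 3 contrasts in 9.1 and the general tests in 9.4.3, though 9.4.3 does not name it |
| Acne, pill continued | Only as an adverse event; not an outcome in section 3 and not a survey topic in 8.1 | None unless serious |
| Any other non-serious event, pill continued | Only as an adverse event | None |

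The last two rows are the gap.

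**2. Would such events occur in 30 women?** The documents give no event rates, so a range is assumed. The chance of seeing at least one event is 1 − (1 − p)^n.

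- p = 5%: 78.5% among 30 women, 40.1% in an arm of 10.
- p = 10%: 1 − 0.9^30 = 95.8% among 30; 1 − 0.9^10 = 65.1% in an arm of 10.
- p = 30%: practically certain among 30, 97.2% in an arm of 10.

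A mild event with a rate of 10% or more would very probably be recorded in the trial.

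**3. Group 3's placebo share.** Section 8.1 starts capsules 120–168 hours after delivery, which is days 5–7. (Section 6.1 gives 120–160 hours, which lies inside that range.) Counting to day 56:

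- start on day 5: 56 − 5 + 1 = 52 capsule days, and 28/52 = 54%;
- start on day 7: 56 − 7 + 1 = 50 capsule days, and 28/50 = 56%.

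More than half of Group 3's capsule time in the study is placebo. Onset is recorded under 8.3.4, so the two periods can be separated.

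**4. What 10 per arm can carry.** With 3 × 10 = 30 women:

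- If 0/10 have an event, the exact two-sided 95% upper limit is 1 − 0.025^(1/10) = 30.8%.
- Fisher's exact test of 0/10 against 4/10 gives p = 0.087, and against 5/10 gives p = 0.033.
- Fisher power at assumed true rates is 6% for 10% v 30%, 30% for 10% v 50%, and 67% for 10% v 70%.

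Tests would miss most differences of interest. Counts with intervals are what the data can support.

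**5. How events come to light.** Section 9.4.4 describes passive recording and 8.3.4 describes enquiry at visits. Section 8.1 has an in-person visit at week 4 and an emailed questionnaire at week 8. If the visit falls on day 28, it covers capsule days 5–28 (24 days) or 7–28 (22 days) of the 28-day first pack. The rest of pack 1 and all of pack 2 come after it, with no later in-person visit described in 8.1. Pack 1 and pack 2 therefore differ in ascertainment as well as in content.

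**The case against.** The strongest reply is that much of the tolerability question has an output elsewhere. Bleeding, one of the two norethindrone side effects named in section 2.2, is a listed outcome with between-group comparisons. Satisfaction, pill use and missed pills are outcomes too. The risks weighed in section 2.3.3 concern milk, breastfeeding and infant growth, all of which have endpoints. Side effects as adverse events appear in the synopsis description and rationale, but not in the Specific Aims or in the hypotheses of section 4.1. This is also a feasibility pilot with 10 per arm. All of that stands, and it limits the point to a reporting gap.

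Three stronger readings are tempting, and the documents do not support them.

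- *That non-serious side effects are never compared between arms.* Bleeding is, and non-serious events that lead to stopping are in the 9.4.4 table.
- *That the table will be nearly empty and will be read as showing minimal side effects.* This needs event rates that the documents do not give. The nearest figure, in section 2.2, is that fewer than half of women intending norethindrone pills use them at 3 months. It gives no reasons for stopping, so it shows neither that such events are rare nor that they are common.
- *That Group 3's placebo events will be counted against delayed drospirenone.* Section 9.4.4 does not say how the table is laid out. Under a comparison of initiation strategies, events in the placebo period properly belong to the assigned arm. The 54% to 56% is a reason to show the periods separately; it does not demonstrate bias.

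It may also be said that all adverse events go to the IRB (8.3.5). Case reporting does not give a summary by arm, so this does not close the gap.

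**Conclusion.** The point holds in a limited form. Section 9.4.4 states a rule that is too narrow for what the study collects and says it will explore: non-serious adverse events other than vaginal bleeding, in women who do not stop the pill, have no planned summary. Even the events that are tabulated are not said to be shown by arm.

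This conclusion comes from reading the sections together and does not depend on any assumed event rate; the rates in the working only indicate that such events are likely to occur. The consequence is confined to safety reporting. The sample size stays at 30 and the primary analysis is unaffected. With 10 women per arm, a fuller table can describe but cannot establish a difference.

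**What to change.** Replace the output sentence in 9.4.4 with wording to this effect:

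> All adverse events will be tabulated by assigned group, as number of women and number of events, by type, maximum severity and relationship. Serious events and events leading to discontinuation of the study pill will be shown as sub-rows. Events will be assigned to pack 1 or pack 2 by recorded onset, so that Group 3's placebo and drospirenone periods appear separately. Proportions of women will be given with exact 95% intervals. No tests will be done.

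Three further edits belong with it.

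- Reconcile the passive recording in 9.4.4 with the enquiry at visits in 8.3.4, so that one rule governs how events are ascertained in every arm.
- State that ascertainment differs between the in-person week 4 visit and the emailed week 8 survey, so a pack 1 to pack 2 comparison within Group 3 mixes drug with method of enquiry.
- If Groups 1 and 3 are set side by side for pack 1, label this as drospirenone against placebo. It is a different question from the timing comparison in 9.1, though both groups are then observed over the same weeks and in the same way.

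The cost is a paragraph of protocol text and a longer table, built from the items that 8.3.4 already requires. The downside is many small counts that must be read descriptively. Reconciling the recording rule may add a little to the enquiry itself, because the survey topics in 8.1 do not list acne or general side effects.

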### 9.4.5 BASELINE DESCRIPTIVE STATISTICS

Baseline characteristics such as demographic information (age, education level, race, ethnicity and employment status) will be collected. At the time of enrollment, questions will also be asked about pregnancy history, past use of contraception, use of donor milk and current perception of adequacy of

human milk supply. Means and proportions of respondents in each of the two groups will be compared to assess for success of randomization.

#### 9.4.6 PLANNED INTERIM ANALYSES

Interim analyses are not planned during this short pilot study.

### 10 SUPPORTING DOCUMENTATION AND OPERATIONAL CONSIDERATIONS

#### 10.1 REGULATORY, ETHICAL, AND STUDY OVERSIGHT CONSIDERATIONS

##### 10.1.1 STUDY DISCONTINUATION AND CLOSURE

This study may be temporarily suspended or prematurely terminated if there is sufficient reasonable cause. Written notification, documenting the reason for study suspension or termination, will be provided by the suspending or terminating party to study participants, investigator and funding agency. If the study is prematurely terminated or suspended, the Principal Investigator (PI) will promptly inform study participants, the Institutional Review Board (IRB), and sponsor and will provide the reason(s) for the termination or suspension. Study participants will be contacted, as applicable, and be informed of changes to study visit schedule.

Circumstances that may warrant termination or suspension include, but are not limited to:

- Determination of unexpected, significant, or unacceptable risk to participants
- Demonstration of efficacy that would warrant stopping
- Insufficient compliance to protocol requirements
- Data that are not sufficiently complete and/or evaluable
- Determination that the primary endpoint has been met
- Determination of futility

Study may resume once concerns about safety, protocol compliance, and data quality are addressed, and satisfy the sponsor and/or IRB.

##### 10.1.3 SAFETY OVERSIGHT

Safety oversight will be monitored by the study PI.

#### 10.1.4 CLINICAL MONITORING

Data verification will take place periodically. This will ensure data completeness and monitor safety of participants.

#### 10.1.5 DATA HANDLING AND RECORD KEEPING

##### 10.1.5.1 DATA COLLECTION AND MANAGEMENT RESPONSIBILITIES

Data collection is the responsibility of the clinical trial staff at the site under the supervision of the PI. The investigator is responsible for ensuring the accuracy, completeness, legibility, and timeliness of the data reported.

##### 10.1.5.2 STUDY RECORDS RETENTION

Study documents will be retained for 2 years after the formal completion of the study.

#### 10.1.6 PROTOCOL DEVIATIONS

It is the responsibility of the PI to use continuous vigilance to identify and report deviations. Protocol deviations must be sent to the reviewing Institutional Review Board (IRB) per their policies. The site investigator is responsible for knowing and adhering to the reviewing IRB requirements.

